Study Design: Describe the research design, including a description of any new methodology and its advantage over existing methodologies.

This is a randomized paired cross-over study in which each subject will undergo MR thermometry with and without active cooling to assess the effect of surface neck cooling on brain temperature.

Procedures: Describe all procedures (sequentially) to which human participants will be subjected. Identify all procedures that are considered experimental and/or procedures performed exclusively for research purposes. Describe the types, frequency and duration of tests, study visits, interviews, questionnaires, etc.

Note: A clinical research protocol may involve interventions that are strictly experimental or it may involve some aspect of research (e.g., randomization among standard treatments for collection and analysis of routine clinical data for research purposes). It is important for this section to distinguish between interventions that are experimental and/or carried out for research purposes versus those procedures that are considered standard therapy. In addition, routine procedures performed solely for research purposes (e.g., additional diagnostic/follow-up tests) should be identified.

Once a subject has been consented, they will schedule a visit at the UVM MRI Center for Biomedical Imaging. The study coordinator will contact the subject 24-48 hours prior to the scheduled visit to complete a COVID-19 Assessment to confirm eligibility to come to campus. After safety to come to campus is confirmed, the study coordinator will meet the subject at an agreed upon location at the UVM Medical Center (e.g. the lobby of the MRI Research Center). Once at the MRI Research Center they will review the MRI Safety Questionnaire and ask whether any changes have occurred since it was completed. All questions will be answered before proceeding.

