	Review of retrospective data		Diaries		Tissue (obtained for clinical purposes)
	Recording of Identifiable Data		Pregnancy Tests		Tissue (obtained solely for research)
	Electrocardiograms				
	Sensitive Data (criminal or sexual conduct, drug or alcohol conduct or use)			(specify):	

**If genetic information is being collected, GINA language must be added to the consent form.

*Deception typically involves withholding information from the potential subject and would require an alteration to the consent process.

Statistical Considerations: Delineate the precise outcomes to be measured and analyzed. Describe how these results will be measured and statistically analyzed. Delineate methods used to estimate the required number of subjects. Describe power calculations if the study involves comparisons. Perform this analysis on each of the primary and secondary objectives, if possible.

Primary outcome: Change in brain temperature

The analytic goal is to describe the change in brain temperature with application of cooling. Brain temperature is a continuous variable. We will use a difference-of-differences model where each subject contributes changes in brain temperature both with and without active cooling where:

$$\Delta T_k = (T_{CE,k} - T_{CB,k}) - (T_{WE,k} - T_{WB,k})$$

ΔT_k = net change in brain temperature for subject k

$T_{CE,k}$ = ending brain temperature, cold intervention for subject k

$T_{CB,k}$ = beginning brain temperature, cold intervention for subject k

$T_{WE,k}$ = ending brain temperature, warm intervention for subject k

$T_{WB,k}$ = beginning brain temperature, warm intervention for subject k

$$H_0: \sum \Delta T_k \neq 0$$

Assuming a significance level of 0.05, power of 0.90, and standard deviation of 0.8 °C (twice the size of previously published values^{Ref}), Student t test requires 13 subjects to detect a change of 0.8 °C. We plan to enroll 15 subjects to allow for loss to follow-up between the two visits.

Ref: Curran EJ, Wolfson DL, Watts R, Freeman K. Cold Blooded: Evaluating Brain Temperature by MRI During Surface Cooling of Human Subjects. *Neurocritical care*. 2017;27(2):214-219.

Secondary outcome: Describe how anthropomorphic characteristics affect change in brain temperature

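### Does printing the primary null hypothesis with a not-equal sign, on a sum, conflict with the t test that sizes the trial?

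*Combined protocol and SAP*

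**What the plan says.** Study Design describes the trial in these words: "This is a randomized paired cross-over study in which each subject will undergo MR thermometry with and without active cooling". Under Statistical Considerations, Primary outcome, the analysis is set out as follows: "We will use a difference-of-differences model where each subject contributes changes in brain temperature both with and without active cooling". ΔT_k is the end-minus-beginning change in the cold session minus the same change in the warm session, and it is labelled "net change in brain temperature for subject k".

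One displayed hypothesis follows, H0: ΣΔT_k ≠ 0. No alternative hypothesis is written.

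The next sentence gives the sizing. It starts "Assuming a significance level of 0.05", sets power at 0.90, takes a "standard deviation of 0.8 °C (twice the size of previously published values"), and concludes that "Student t test requires 13 subjects to detect a change of" 0.8 °C. Enrolment is then set: "We plan to enroll 15 subjects to allow for loss to follow-up between the two visits".

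The protocol states no other primary hypothesis. For the secondary outcome it says that no formal testing is planned.

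**The concern.** The displayed line looks wrong in two ways. First, a null hypothesis for a t test is an equality, because alpha is the rejection probability when the mean is zero. A statement that something differs from zero is the alternative. Second, ΣΔT_k is a quantity computed from the subjects who happen to be enrolled, whereas a hypothesis should concern a population parameter such as the mean of ΔT.

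The alternative, the sidedness and the direction that counts as success are also not written out. Since this is the trial's only formal test, a reader could fear two things: that a significant result would be read as rejecting the existence of a change, or that sidedness could be chosen after the data are seen. If either happened, the headline conclusion would be at stake.

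**Working it through.** **Inputs**, all from Statistical Considerations, Primary outcome: alpha 0.05, power 0.90, SD 0.8 °C, change to detect 0.8 °C, required n = 13, planned enrolment 15. The SD is taken as the SD of ΔT_k, which the protocol does not spell out. The standardised effect is d = 0.8/0.8 = 1.

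**1. Which test gives 13?** For a one-sample t test of mean ΔT = 0, power is the probability that a noncentral t variable with n − 1 degrees of freedom and noncentrality d√n falls beyond the critical value. At n = 13 the noncentrality is 1 × √13 = 3.606.

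| Reading | n required | Power |
|---|---|---|
| Two-sided 0.05, exact t | 13 | 0.911 (n = 12: 0.883; n = 15: 0.949) |
| One-sided 0.05, exact t | 11 | 0.924 (n = 10: 0.898) |
| Two-sided, normal approximation | 11 | – |
| One-sided, normal approximation | 9 | – |
| Unpaired two groups, normal approximation | 22 per group two-sided, 18 one-sided | – |

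Of these readings, only the two-sided one-sample t test of zero mean change gives the plan's 13. The figure therefore identifies both the intended null and the intended sidedness.

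**2. Does the sum matter?** With sample mean m and sample SD s, the t statistic for the mean is m/(s/√n). The sum is nm, and its standard error is s√n, so its t statistic is nm/(s√n) = m√n/s, which is the same quantity. A simulated sample of 13 gave −4.701 in both forms. The sum is loose notation and has no numerical effect.

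**3. Could the printed null be applied as written?** No. Rejecting an inequality in favour of equality needs an equivalence margin, and none is given. The sizing sentence names a t test whose purpose is "to detect a change of 0.8 °C". Rejection under that test therefore means that a change was detected, and the stated alpha and power have meaning only if the null is zero change. No coherent procedure leads from the printed line to a reversed conclusion.

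**4. Is the direction open?** ΔT_k = (cold end − cold beginning) − (warm end − warm beginning). If the brain cools more in the cold session, the first bracket is the lower and ΔT_k is negative. The definition fixes the sign.

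**5. How much hangs on the unwritten sidedness?** At n = 13 and SD 0.8 °C, the standard error is 0.8/√13 = 0.222 °C. The two-sided test is significant when the observed mean exceeds 2.179 × 0.222 = 0.483 °C in size, which is also the half-width of the 95% confidence interval. The one-sided threshold is 1.782 × 0.222 = 0.395 °C. Only an observed mean cooling between about 0.40 and 0.48 °C would be judged differently, and the effect planned for is 0.8 °C.

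**The case for a change.** The strongest case for amending the text is that this line is the only formal hypothesis in the protocol and that, as printed, it is wrong. The stated aim is to describe, but the plan also sets alpha and power and uses the body-temperature session to attribute any change to the water temperature. That is an inferential claim and deserves a correctly written null. The t test is named only in the sizing sentence, so an analyst must join the two. Writing the hypotheses and sidedness in full would take two lines and would close off a later choice of a one-sided test.

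Part of this stands. The relation sign is wrong for a null, and the sidedness is not written. The text was read from a PDF by a program, so a misread equals sign cannot be excluded, but nothing points to one and little weight rests on it.

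The argument fails on consequence. Joining the per-subject ΔT_k to the t test in the following sentence takes no invention, because the required n confirms the link. A later move to one-sided 0.05 would be visible against a stated 13 that fits only the two-sided test. A printed confidence interval and an explicit rule that cooling needs a negative mean would be reasonable additions, but they do not correct any result that the plan would produce.

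**Conclusion.** The concern does not call for a change to the plan. The not-equal sign is a clerical slip, the sum is harmless notation, and the missing alternative and sidedness are details that the plan's own sample size supplies. Under the evident reading, a two-sided one-sample t test of mean ΔT = 0 at 0.05, the requirement is 13 with power 0.911. Enrolment of 15 gives 0.949 if all complete. The estimate, test statistic, p-value and conclusion are the same with the symbol corrected or left alone.

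This rests on two assumptions: that 0.8 °C is the SD of ΔT_k, and that two-sided testing was intended. The second is inferred from the match to 13. Whether 0.8 °C is a sound SD for ΔT is a separate question, which the wording of the hypothesis does not affect.
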